Sampling and sample size; Any SHCP currently studying and working in COVID-19 units. Pilot research identified significant impact on student communication and a medium effect size is expected. Using Cohen's (1988) tables with an alpha of 0.01, $d = 0.5$ (a medium effect) and beta of 0.9 we will recruit 94 SHCP per group to take part in this research. This will give a total of 120 SHCP and we will add in a 10% margin ($n=20$) for dropout or incomplete data. This gives a total of 140 SHCP to be randomised per arm or 280 in total. We will try and ensure a mixed sample with SHCP from different allied health professional groups using purposive sampling.

Sequence generation; Random number calculator with randomly selected block sizes (Efird, 2011).

Allocation concealment; undertaken by e-links not known to the researcher

Sequence generation; We will replicate the pilot research and include a random number calculator with randomly selected block sizes (Efird, 2011). Randomisation undertaken by a member of the research team separate from the study will allocate SHCP to an intervention control group using a random number generator.

Blinded assessor; Only blinded assessment will take place. Before randomisation a blinded assessor (lecturer in physiotherapy or research student) will distribute questionnaires. The pre-recorded e-learning programme has been prepared by [name] who developed and prepared all pilot studies. Following the completion of the training an assessor who is blinded to treatment arm will organise and collect follow-up assessments.

Data collection methods: Before data collection starts SHCP will be shown the information sheet via email and asked to consent (Appendix B). A baseline measurement will take place (Appendix C). The baseline measurement will take place over a secure electronic data capture system called Research Electronic Data Capture (REDCap). Following this, students in each group will receive the training. Once the training is complete students will again fill in the measurement tools using REDCap. The research associate will send out two email reminders to any participant who doesn't fill in the forms.

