Intervention: The SIT intervention will include a single screening interview taking 20 minutes with [name]. Following this the participant will be sent a pre-recorded e-based training session. The lecture takes 45 minutes. The indicative content considers examples of interactions, the science behind the MEAH, the use of screening and how to engage in a brief narrative-based intervention within practice. It has the same components as the pilot studies, although adapted into one training session. The final part of the training for SHCP will include an e-learning presentation. The presentation will provide an analysis of the screening calls. This will reveal the most common difficulties and stories expressed within screening and will

summarise the difficulties that were challenging to adapt to, illustration of how the MEAH is important for this understanding and the most common coping strategies identified (this was undertaken and achieved as part of the pilot research to consolidate learning). The principles are that sharing this information will provide direct access to others experiences which has been associated with enhanced mental health outcomes (Ooms et al., 2016; Soundy et al., 2019). The benefit of this is SHCP can access effective coping strategies that promote mental health and psychological well-being outcomes. This entire process will take a maximum of two hours to complete at a pace and time that is convenient to the participant.

Inactive control group 1: an inactive waiting list control group will be used. Individuals in this group will receive or be offered the SIT intervention at week 12.

Active control group 2: an alternative e-intervention will be used which includes a 45 minutes pre recorded lecture. Individuals in this group will receive or be offered the SIT intervention at week 12.

Outcome measures for SHCP;

See Appendix C for all outcome measures

Demographics; Age, gender, professional group, type of course, year of course. Time experience of working in a COVID-19 setting in months.

Primary outcome measure for SHCP:

The Hospital Anxiety and Depression Scale (HADS: Zigmond and Snaith, 1983). A 14-Item questionnaire that assesses depression and anxiety.

Secondary outcomes measures for SHCP;

(a) The SF-12 Quality of life questionnaire (Ware et al., 1995). A 12-item questionnaire that assesses quality of life.

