24-week intervention group follow up completed by: May 2021 (analysis completed by trials unit other staff costs covered by University)

Follow up publication: June 2021

Other publications: September 2021.

Data management: The research associated will use the University REDCap system to access the data and only work on a University password protected computer.

Statistical methods; For the main study and sub-study descriptive statistics will be used. Confidence intervals will be used to consider change. A factorial ANOVA (a parametric statistical technique which can assess change in one test rather than needing to perform many) will be used to test group differences across outcome measures. An ANOVA will consider the change in scores across time for the intervention group. All qualitative data will be analysed using a thematic analysis (Braun and Clarke, 2006).

Data monitoring: [name] will report any adverse events to University program leader for consideration. Any program leader will be able to stop the study if required. No adverse events were reported across all pilot research. All adverse events will be reported to the steering group committee.

Ethics: We will adhere to the; Research Governance Framework (Department of Health 2005), Declaration of Helsinki (World Health Association, 2013) and University of Birmingham Code of Practice for research (University of Birmingham 2018) and General Data Protection Regulation (2018).

Protocol amendments: [name] will report any protocol amendments.

Consent: the research associate will ensure consent is obtained from participants.

Confidentiality: All data will be stored anonymously on the University of Birmingham computer. Declaration of interest: None are declared.

Access to data: only the research team will have access to the full data.

Ancillary and post-trial care: This will be reported by [name] to program leads if required.

Deliverables

Benefits within the Hospital setting

- Reduced depression and anxiety across SHCP
- Positive changes in hope, psychological adaptation and emotions in relation to a specified difficulty
- Increased resilience and decreased burn out in staff
- Enhanced interactions that are supportive and able to empower patients to be more autonomous
- Increased patient satisfaction
- Potential to decrease reliance on pharmacological approaches
- Reduced work absence and improved work productivity
- Identification of basic NHS-related cost savings

[figure not shown]

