Appendix A

Initial Email Advertising training

Subject Title: Mental Health Screening, intervening and Training (SIT) of Health Care Professionals; a randomised control trial

Message content:

We are looking for student health care professionals to take part in a new study designed to support mental health and patient interaction.

The assessments if you joining the study take a total of 10 minutes on three occasions (pre, post and 12-week follow up)

IF you take part in the study you could be allocated to a control group or intervention group

If you get allocated to the intervention group:

The total training time takes 2 hours that can be completed at a self-pace online (undertaken as suits you). The training has 3 parts

- 1. Arrange a e-based screening call with [name] (zoom or skype or telephone) to support you and your mental health**
- 2. Watch a pre-recorded 45 lecture to train you**
- 3. Consider a summary e-presentation of the responses given across health care professionals to part 1.**

If you get allocated to the control group

You will either view a 45 minute lecture or be allocated to a no treatment control

Document provided to participants if it is identified that they are distressed or become concerned following the intervention.

Appendix C: Questionnaire pack given across email to SHCP at pre-post and follow up time points trial.

Unique Identification Number Generated for you: MEAH 02 A (CHANGED FOR EACH PARTICIPANT)

Please complete this questionnaire which asks specific questions about the course content and your reflections of the value of the course.

PLEASE NOTE BY COMPLETING THIS QUESTIONNAIRE YOU ARE PROVIDING CONSENT FOR YOUR PARTICIPATION. Please contact [name] should you want your data removed by 1 August 2020.

Demographics

Age (Years)	
Gender	
Name of Profession (e.g., Nurse, Physiotherapist)	
Type of Course: BSc, MSc	
Year of Course:	
Have you had experience within a COVID-19 unit	Yes / No
Have you had experience of caring for people with COVID-19 as part of your role	Yes / No
Have you had past teaching or experience related to psychological adaptation, hope, emotions or illness stories (narratives)? (circle one)	YES / NO

Hospital Anxiety and Depression Scale (HADS)

Tick the box beside the reply that is closest to how you have been feeling in the past week. Don't take too long over you replies: your immediate is best.

I feel tense or 'wound up':

Most of the time	3
A lot of the time	2

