Appendix E Semi-structured interview

Section 1: General questions

Can you tell me about your experience of taking part in this intervention?

Would you recommend this intervention? If so, to who and why? OR if not why not?

Was there anything that stood out about it? Can you explain what that was?

Section 2: Perception and experiences of the intervention

What was good or not so good about this intervention? Can you explain why?

Were there any benefits associated with taking the intervention? Can you explain what these were OR can you identify why there weren't any?

Did the e-application of the intervention work from your perspective? Can you explain your answer?

Was the length of time and level of content appropriate? Can you explain your answer?

Have you changed anything you were doing as a result of the intervention? Can you explain what this was?

Have you used aspects of the intervention in clinical practice? If so, how? Can you explain your answer?

From the above questions about the intervention, if there were to be changes to the intervention what should these be?

Section 3: Future application of the intervention

Do you think the intervention should be used for physiotherapists more widely? Can you explain why?

Do you think the intervention could be used in clinical placement education training settings? I.e. whilst you go on placement? Can you explain your answer?

Do you think the intervention could be integrated into a university course? Can you explain your answer?

*Appendix F: The Model of Emotions, Hope and Adaptation Screening Tool
Version 3.4*

Participant ID: MEAH COVID P

Hope and Adaptation Questions

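### Adverse events are to be reported to the steering group, but no instrument asks every arm about them, and only SIT participants have a live contact before week 12

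*Protocol*

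**What the plan says.** **Reporting route (Data monitoring).** A team member "will report any adverse events to University program leader for consideration", and "All adverse events will be reported to the steering group committee". Any program leader may stop the study. The section also says of the earlier work that "No adverse events were reported across all pilot research". It does not define an adverse event, set a time window or say how events come to light.

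**Instrument common to all arms.** This is headed "Appendix C: Questionnaire pack given across email to SHCP at pre-post and follow up time points trial". It holds demographics, HADS, SF-12, MEAH, the interpersonal reactivity index, the open minds scale, the Froehlich survey and the Adult Hope Scale. Under Blinded assessor, "Following the completion of the training an assessor who is blinded to treatment arm will organise and collect follow-up assessments".

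**Live contact.** Under Intervention, "The SIT intervention will include a single screening interview taking 20 minutes". Inactive control group 1 is a waiting list and Active control group 2 receives a recorded lecture. Both are given or offered SIT at week 12. A semi-structured interview is planned at week 12. Its schedule (Appendix E) includes "What was good or not so good about this intervention? Can you explain why".

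**Analysis.** Under Statistical methods, a factorial ANOVA "will be used to test group differences across outcome measures". Adverse events are not mentioned there.

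**The concern.** A report to the program leader or steering group can only follow if someone on the team hears of an event. If nobody asks, that depends on participants volunteering it, and the opportunity to do so differs by arm. A SIT participant speaks to a team member for 20 minutes about a current personal difficulty. Before week 12 a control participant has only emails, questionnaires and, in one arm, a recording.

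Two things are at stake. First, if the steering group or a later report sets event counts side by side by arm, a difference could reflect contact rather than harm. Second, a statement that no adverse events occurred, like the one made for the pilots, would say little about the controls, because nobody had asked them. A later analysis plan cannot repair this: events that were never asked about cannot be recovered at analysis.

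**Working it through.** The protocol gives no adverse-event rate or harms calculation to reproduce, so the check is mainly textual.

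**1. Is there an adverse-event item in the common pack?** Going through Appendix C instrument by instrument, none asks about an adverse experience, a crisis or help sought since the last assessment.

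**2. Who has live contact before week 12?**

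| Arm | Contact described before week 12 |
|---|---|
| SIT | 20-minute call, recorded lecture, e-presentation, questionnaires |
| Inactive control | Questionnaires and email reminders |
| Active control | Recorded lecture, questionnaires and email reminders |

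**3. Do the live contacts ask about harm?** Not directly. Appendix D explores the impact and course of a self-named difficulty and the feelings attached to it. Appendix E asks for views on the intervention. The call opens the intervention, before the lecture, so it can reveal distress present at the time but not harm arising later. The interview is for student health care professionals with no arm named. The wording of Appendix E suggests people who received an intervention, but that is an inference.

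**4. What do the symmetric scales cover?** HADS asks about the past week, SF-12 mostly about the past 4 weeks, and MEAH about right now. In the 12-week pack the longest window therefore reaches back to week 12 − 4 = 8, and HADS to week 12 − 1 = 11. An episode at week 4 that had resolved by week 8 would leave no direct record there. Nor does Data monitoring route a worsened score to the program leader or steering group.

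**5. How large could the distortion be?** Let the true risk be p in both arms, with capture probabilities c₁ (SIT) and c₀ (control). The observed risk ratio is

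(p × c₁) / (p × c₀) = c₁ / c₀,

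whatever p and the arm size. For illustration only, take p = 0.10 and 140 per arm, the figure under Sampling and sample size. Both p and the capture probabilities are assumptions.

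| c₁ | c₀ | Expected reports, SIT | Expected reports, control | Ratio |
|---|---|---|---|---|
| 0.5 | 0.5 | 140 × 0.10 × 0.5 = 7.0 | 7.0 | 1.0 |
| 0.6 | 0.4 | 140 × 0.10 × 0.6 = 8.4 | 140 × 0.10 × 0.4 = 5.6 | 1.5 |
| 0.6 | 0.3 | 8.4 | 140 × 0.10 × 0.3 = 4.2 | 2.0 |

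The output only restates the assumed capture ratio. It shows how the bias would work; it does not estimate it.

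**The case against.** The strongest reply is that no harms comparison exists to be biased. The planned group tests concern outcome measures, and adverse events travel as individual reports; no tabulation by arm or stopping decision based on relative counts is stated. That stands, and it limits the point to how comparable any by-arm reading would be.

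A reader might go further and infer that the plan searches for events in SIT and merely waits in the other arms, that both live contacts are exclusive to SIT, or that SIT would show a several-fold excess. The documents support none of these. Neither script asks about adverse events, the call precedes the lecture, the interview is not assigned to an arm, and controls can have the same call once they receive SIT at week 12. Any multiple is the ratio of two assumed capture rates.

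It is also fair to say that psychological worsening, the most plausible harm of a two-hour talking and e-learning package, is measured identically in every arm up to 12 weeks, with follow-up collected by a blinded assessor. That is real mitigation. It does not cover short episodes outside the recall windows, or help sought.

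Lastly, a line just before Appendix C mentions a support document for participants identified as distressed or concerned after the intervention, without saying how they are identified. The information and consent pages are not in the text available, so a reporting instruction given to all arms may exist there. It would still rely on spontaneous reporting.

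**Conclusion.** The point holds in a limited form. The protocol fixes a common questionnaire pack without an adverse-event or help-sought item, promises that all events will be reported, and describes live contact before week 12 in one arm only. Counts by arm would therefore not be safely comparable, and an absence of reports among controls would not be informative. The size is unknown and could be nil if the call brings out nothing extra. The conclusion rests on the Appendix C text as shown and on no other routine contact with controls existing. The primary efficacy analysis is unaffected. This is a cheap improvement to data collection that has to be made before the data are collected.

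**What to change.** - Add one identical item to the REDCap pack at post and 12 weeks in all three arms: any adverse experience or help sought since the last questionnaire, with the date.
- Base any by-arm summary of adverse events on those reports only, for the period before controls receive SIT at week 12.
- List events heard in calls or interviews separately. They still go to the program leader and steering group.
- Tabulate by arm, up to 12 weeks, the proportion whose HADS score worsened from baseline. These data are already collected equally.

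The item need not be extended to 24 weeks in all arms, because the Participant timeline labels that follow-up as intervention group.

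Cost: about a minute more per questionnaire, on a pack stated to take about 10 minutes, and one extra table. No additional staff are needed.

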Appendix A

Initial Email Advertising training

Subject Title: Mental Health Screening, intervening and Training (SIT) of Health Care Professionals; a randomised control trial

Message content:

We are looking for student health care professionals to take part in a new study designed to support mental health and patient interaction.

The assessments if you joining the study take a total of 10 minutes on three occasions (pre, post and 12-week follow up)

IF you take part in the study you could be allocated to a control group or intervention group

If you get allocated to the intervention group:

The total training time takes 2 hours that can be completed at a self-pace online (undertaken as suits you). The training has 3 parts

- 1. Arrange a e-based screening call with [name] (zoom or skype or telephone) to support you and your mental health**
- 2. Watch a pre-recorded 45 lecture to train you**
- 3. Consider a summary e-presentation of the responses given across health care professionals to part 1.**

If you get allocated to the control group

You will either view a 45 minute lecture or be allocated to a no treatment control

Document provided to participants if it is identified that they are distressed or become concerned following the intervention.

Appendix C: Questionnaire pack given across email to SHCP at pre-post and follow up time points trial.

Unique Identification Number Generated for you: MEAH 02 A (CHANGED FOR EACH PARTICIPANT)

Please complete this questionnaire which asks specific questions about the course content and your reflections of the value of the course.

PLEASE NOTE BY COMPLETING THIS QUESTIONNAIRE YOU ARE PROVIDING CONSENT FOR YOUR PARTICIPATION. Please contact [name] should you want your data removed by 1 August 2020.

Demographics

Age (Years)	
Gender	
Name of Profession (e.g., Nurse, Physiotherapist)	
Type of Course: BSc, MSc	
Year of Course:	
Have you had experience within a COVID-19 unit	Yes / No
Have you had experience of caring for people with COVID-19 as part of your role	Yes / No
Have you had past teaching or experience related to psychological adaptation, hope, emotions or illness stories (narratives)? (circle one)	YES / NO

Hospital Anxiety and Depression Scale (HADS)

Tick the box beside the reply that is closest to how you have been feeling in the past week. Don't take too long over you replies: your immediate is best.

I feel tense or 'wound up':

Most of the time	3
A lot of the time	2
From time to time, occasionally	1
Not at all	0

I still enjoy the things I used to enjoy:

Definitely as much	0
Not quite so much	1
Only a little	2
Hardly at all	3

I get a sort of frightened feeling as if something awful is about to happen:

Very definitely and quite badly	3
Yes, but not too badly	2
A little, but it doesn't worry me	1
Not at all	0

I can laugh and see the funny side of things:

As much as I always could	0
Not quite so much now	1
Definitely not so much now	2
Not at all	3

Worrying thoughts go through my mind:

A great deal of the time	3
A lot of the time	2
From time to time, but not too often	1
Only occasionally	0

I feel cheerful:

Not at all	3
Not often	2
Sometimes	1
Most of the time	0

I can sit at ease and feel relaxed:

Definitely	0
Usually	1
Not Often	2
Not at all	3

I feel as if I am slowed down:

Nearly all the time	3
---------------------	---

Very often	2
Sometimes	1
Not at all	0

I get a sort of frightened feeling like 'butterflies' in the stomach:

Not at all	0
Occasionally	1
Quite Often	2
Very Often	3

I have lost interest in my appearance:

Definitely	3
I don't take as much care as I should	2
I may not take quite as much care	1
I take just as much care as ever	0

I feel restless as I have to be on the move:

Very much indeed	3
Quite a lot	2
Not very much	1
Not at all	0

I look forward with enjoyment to things:

As much as I ever did	0
Rather less than I used to	1
Definitely less than I used to	2
Hardly at all	3

I get sudden feelings of panic:

Very often indeed	3
Quite often	2
Not very often	1
Not at all	0

SF-12®:

Answer every question by placing a check mark on the line in front of the appropriate answer. It is not specific for arthritis. If you are unsure about how to answer a question, please give the best answer you can and make a written comment beside your answer.

1. In general, would you say your health is:

Excellent (1)

Very Good (2)

Good (3)

Fair (4)

Poor (5)

The following two questions are about activities you might do during a typical day. Does YOUR HEALTH NOW LIMIT YOU in these activities? If so, how much?

2. MODERATE ACTIVITIES, such as moving a table, pushing a vacuum cleaner, bowling, or playing golf:

Yes, Limited A Lot (1)

Yes, Limited A Little (2)

No, Not Limited At All (3)

3. Climbing SEVERAL flights of stairs:

Yes, Limited A Lot (1)

Yes, Limited A Little (2)

No, Not Limited At All (3)

During the PAST 4 WEEKS have you had any of the following problems with your work or other regular activities AS A RESULT OF YOUR PHYSICAL HEALTH?

4. ACCOMPLISHED LESS than you would like:

Yes (1)

No (2)

5. Were limited in the KIND of work or other activities:

Yes (1)

No (2)

During the PAST 4 WEEKS, were you limited in the kind of work you do or other regular activities AS A RESULT OF ANY EMOTIONAL PROBLEMS (such as feeling depressed or anxious)?

6. ACCOMPLISHED LESS than you would like:

Yes (1)

No (2)

5. Didn't do work or other activities as CAREFULLY as usual:

Yes (1)

No (2)

8. During the PAST 4 WEEKS, how much did PAIN interfere with your normal work (including both work the home and housework)?

Not At All (1)

A Little Bit (2)

Moderately (3)

Quite A Bit (4)

Extremely (5)

The next three questions are about how you feel and how things have been DURING THE PAST 4 WEEKS. For each question, please give the one answer that comes closest to the way you have been feeling. How much of the time during the PAST 4 WEEKS –

9. Have you felt calm and peaceful?

All of the Time (1)

Most of the Time (2)

A Good Bit of the Time (3)

Some of the Time (4)

A Little of the Time (5)

None of the Time (6)

10. Did you have a lot of energy?

- All of the Time (1)
- Most of the Time (2)
- A Good Bit of the Time (3)
- Some of the Time (4)
- A Little of the Time (5)
- None of the Time (6)

11. Have you felt downhearted and blue?

- All of the Time (1)
- Most of the Time (2)
- A Good Bit of the Time (3)
- Some of the Time (4)
- A Little of the Time (5)
- None of the Time (6)

12. During the PAST 4 WEEKS, how much of the time has your PHYSICAL HEALTH OR EMOTIONAL PROBLEMS interfered with your social activities (like visiting with friends, relatives, etc.)?

- All of the Time (1)
- Most of the Time (2)
- A Good Bit of the Time (3)
- Some of the Time (4)
- A Little of the Time (5)
- None of the Time (6)

The Model of Emotions, Hope and Adaptation Screening Tool
Version 3.3

Participant ID: MEAH COVID P
Hope and Adaptation Questions

Please answer the following five questions. The questions will relate to an aspect of your current situation to which you are finding it difficult to adapt or a challenge. Examples of this include adapting to the following; experiences relating to the process of diagnosis, the impact of the diagnosis, changes or losses in relationships in the workplace, socially or at home, the inability to be independent, and the loss of an identity like being an athlete or father. This assessment and screening tool is designed to identify the need you have for support and is able to track your process of adaptation to the difficulty over time. During subsequent meetings, you may like to track other difficulties or challenges. All information is collected anonymously and may only be used for research and as group feedback to support coping activities. These aspects should benefit your mental health.

Note: The numbers identified on the left-hand side of each scale distinguish responses by a rating relating to hope, adaptation and emotions. Positive or negative numbers further away from zero illustrate a more intense response.

1. Complete the sentence below and name the one aspect of your adaptation that you are finding most difficult?

I am finding considerable/most difficulty adapting to _____

2.Regarding the difficulty you have identified how hopeful are you right now that you can or will overcome it?

Level of Hope associated with difficulty	Circle a number reflecting the statements on the left
I am completely certain and have no doubt that I will be able to overcome this difficulty	+4
I am certain that I will be able to overcome this difficulty	+3
I believe it is likely that I will overcome this difficulty	+2
I believe it is possible to overcome this difficulty	+1
I accept that it might not be possible to overcome this difficulty	0
I feel uncertain and don't know if this difficulty can be overcome	-1
I feel that it is likely that I wont overcome this difficulty	-2
I have little hope or ability to overcome this difficulty	-3
I see neither hope or ability to overcome this difficulty	-4

3. Regarding the difficulty you have identified do you feel able to psychologically adapt to it right now? Circle a number by considering the statements.

Ability to adapt to the difficulty	Circle a number reflecting the statements on the left
I am able to positively embrace and use this difficulty for benefit	+4
I am able to fully accept and embrace this difficulty	+3
I am able to fully accept this difficulty	+2
I acknowledge this difficulty but can't fully accept it	+1
I am able to acknowledge this difficulty	0
I struggle with acknowledging this difficulty	-1
I find it difficult to accept this difficulty	-2
I find it very difficult to accept this difficulty	-3
I reject and cannot accept this difficulty	-4

Mood Questions

Mood or feelings, for the purpose of this study, is considered by using two separate questions.

4. What level of energy do you have today right now with regards to dealing with the difficulty you have identified. Please mark it on a scale from extremely high to extremely low

Energy Level to deal with the difficulty	Circle a number reflecting the statements on the left
I feel very highly energised to deal with this difficulty	+4
I feel highly energised to deal with this difficulty	+3
I feel moderate levels of energy to deal with this difficulty	+2
I feel above average levels of energy to deal with this difficulty	+1
I feel average or normal levels of energy to deal with this difficulty	0
I feel below average levels of energy to deal with this difficulty	-1
I feel moderately low levels of energy to deal with this difficulty	-2
I feel little energy available to deal with this difficulty	-3

I feel very little energy available to deal with this difficulty	-4
------------------------------------------------------------------	----

5. Please score how you feel about the difficulty you have identified in a range from pleasant to unpleasant

Valence or Pleasantness on how you feel about the difficulty	Circle a number reflecting the statements on the left
I have extremely positive feelings regarding the difficulty I am facing	+4
I have positive feelings regarding the difficulty I am facing	+3
I have pleasant feelings regarding the difficulty I am facing	+2
I have above average feelings regarding the difficulty I am facing	+1
I have average or normal feelings regarding the difficulty I am facing	0
I have below average feelings regarding the difficulty I am facing	-1
I have below average or unpleasant feelings regarding the difficulty I am facing	-2
I have negative feelings regarding the difficulty I am facing	-3
I have extremely negative feelings regarding the difficulty I am facing	-4

Interpersonal reactivity index

Source: Davis (1980, 1983).

Please indicate the extent that each statement describes you, using the following scale: 01234
(does not describe me well) (describes me very well)

Scoring	0 (does not describe me well)				
	4 (describes me very well)				
Fantasy Scale	0	1	2	3	4
When I am reading an interesting story or novel, I imagine how I would feel if the events in the story were happening to me.					
I really get involved with the feelings of the characters in a novel.					
I am usually objective when I watch a movie or play, and I don't often get completely caught up in it.*					
After seeing a play or movie, I have felt as though I were one of the characters.					
I daydream and fantasize, with some regularity, about things that might happen to me					
Becoming extremely involved in a good book or movie is somewhat rare for me.*					
When I watch a good movie, I can very easily put myself in the place of a leading character.					
Scoring	0 (does not describe me well)				
	4 (describes me very well)				
Perspective-Taking Scale	0	1	2	3	4
Before criticizing somebody, I try to imagine how I would feel if I were in their place.					
If I'm sure I'm right about something, I don't waste much time listening to other people's arguments.*					
I sometimes try to understand my friends better by imagining how things look from their perspective.					
I believe that there are two sides to every question and try to look at them both.					
I sometimes find it difficult to see things from the other person's point of view.*					
I try to look at everybody's side of a disagreement before I make a decision.					
When I'm upset at someone, I usually try to "put myself in their shoes" for a while.					
Scoring	0 (does not describe me well)				
	4				

	(describes me very well)				
Empathetic Concern	0	1	2	3	4
When I see someone being taken advantage of, I feel kind of protective toward them.					
When I see someone being treated unfairly, I sometimes don't feel very much pity for them.*					
I often have tender, concerned feelings for people less fortunate than me.					
I would describe myself as a pretty soft-hearted person.					
Sometimes I don't feel sorry for other people when they are having problems.*					
Other people's misfortunes do not usually disturb me a great deal.*					
I am often quite touched by things that I see happen.					
Scoring	0 (does not describe me well) 4 (describes me very well)				
Personal Distress Scale	0	1	2	3	4
When I see someone who badly needs help in an emergency, I go to pieces.					
I sometimes feel helpless when I am in the middle of a very emotional situation.					
In emergency situations, I feel apprehensive and ill-at-ease.					
I am usually pretty effective in dealing with emergencies.*					
Being in a tense emotional situation scares me.					
When I see someone get hurt, I tend to remain calm.*					
I tend to lose control during emergencies.					

Note: Labels should be removed and items randomly ordered prior to administration. Items marked with an asterisk (*) are reverse-scored. After reverse scoring, scores from each subscale are averaged.

Open Minds Scale for Health Care Providers (OMS-HC-15)

Question	Strongly disagree	Disagree	Neither agree or disagree	Agree	Strongly agree
I am more comfortable helping a person who has a physical illness than I am helping a person who has a mental illness.					
If a colleague with whom I work told me they had a mental illness, I would be just as willing to work with him/her.					
If I were under treatment for a mental illness I would not disclose this to any of my colleagues.					
I would see myself as weak if I had a mental illness and could not fix it myself.					
I would be reluctant to seek help if I had a mental illness.					
Employers should hire a person with a managed mental illness if he/she is the best person for the job.					
I would still go to a physician if I knew that the physician had been treated for a mental illness.					
If I had a mental illness, I would tell my friends.					
Despite my professional beliefs, I have negative reactions towards people who have mental illness.					
There is little I can do to help people with mental illness.					
More than half of people with mental illness don't try hard enough to get better.					
I would not want a person with a mental illness, even if it were appropriately managed, to work with children.					

Healthcare providers do not need to be advocates for people with mental illness.					
I would not mind if a person with a mental illness lived next door to me.					
I struggle to feel compassion for a person with mental illness.					

Froehlich Communication Survey

Name

Developing effective interpersonal communication is an ongoing process. The purpose of this survey is to help you identify your strengths, areas for improvement and goals related to effective interpersonal communication. Please circle the number that best reflects your agreement with the following statements so you can clarify where you need to work to be a more effective communicator.

I Strongly Disagree
Disagree
Agree
IO Strongly Agree

Much Improvement Needed
Moderate Improvement Needed
Some Improvement Needed
Little Improvement Needed

I can listen without interrupting.	1	2	3	4	5	6	7	8	9	10
I can keep my mind free of distractions while listening.	1	2	3	4	5	6	7	8	9	10
I can allow for silence.	1	2	3	4	5	6	7	8	9	10
When appropriate, I can offer steady eye contact while listening.	1	2	3	4	5	6	7	8	9	10
I am aware of body language while listening.	1	2	3	4	5	6	7	8	9	10
My posture and facial expression show interest and caring.	1	2	3	4	5	6	7	8	9	10
I don't fidget while listening.	1	2	3	4	5	6	7	8	9	10
I can build rapport with others.	1	2	3	4	5	6	7	8	9	10
I appropriately maintain confidentiality.	1	2	3	4	5	6	7	8	9	10
I can maintain compassion while listening.	1	2	3	4	5	6	7	8	9	10
I use open and closed-ended questions to determine someone's concerns and goals.	1	2	3	4	5	6	7	8	9	10
I can effectively use restatement, summaries and clarification in a conversation.	1	2	3	4	5	6	7	8	9	10
I can identify, reflect and validate emotional and verbal content in a conversation.	1	2	3	4	5	6	7	8	9	10
I can maintain mental focus when listening to someone who is upset.	1	2	3	4	5	6	7	8	9	10
I can convey hopefulness.	1	2	3	4	5	6	7	8	9	10
I can use humor effectively.	1	2	3	4	5	6	7	8	9	10
I can judge when to use touch during conversations.	1	2	3	4	5	6	7	8	9	10

I can judge when to redirect someone or help someone get their attention off their distress in a conversation.

1 2 3 4 5 6 7 8 9 10

I can judge when someone is ready to hear information or advice.

1 2 3 4 5 6 7 8 9 10

I am clear, concise and confident when I speak.

1 2 3 4 5 6 7 8 9 10

I can give, receive and solicit constructive feedback including appreciation of others and myself.

1 2 3 4 5 6 7 8 9 10

I can be appropriately assertive in interactions with others.

1 2 3 4 5 6 7 8 9 10

I communicate well on teams by listening to multiple perspectives and sharing mine.

1 2 3 4 5 6 7 8 9 10

I understand the importance of seeking an interpreter when I don't understand the language of a client.

1 2 3 4 5 6 7 8 9 10

I can communicate effectively with people from different racial and cultural groups.

1 2 3 4 5 6 7 8 9 10

Score /250

Adult Hope Scale (Synder, 1991)

Directions: Read each item carefully. Using the scale shown below, please select the number that best describes YOU and put that number in the blank provided.

1. = Definitely False 2. = Mostly False 3. = Somewhat False 4. = Slightly False

5. = Slightly True 6. = Somewhat True 7. = Mostly True 8. = Definitely True

1. I can think of many ways to get out of a jam. ____
2. I energetically pursue my goals.
3. I feel tired most of the time.
4. There are lots of ways around any problem. ____
5. I am easily downed in an argument.
6. I can think of many ways to get the things in life that are important to me.
7. I worry about my health.
8. Even when others get discouraged, I know I can find a way to solve the problem. ____
9. My past experiences have prepared me well for my future.
10. I've been pretty successful in life.
11. I usually find myself worrying about something.
12. I meet the goals that I set for myself.

Scoring:

Items 2, 9, 10, and 12 make up the agency subscale. Items 1, 4, 6, and 8 make up the pathway subscale.

Researchers can either examine results at the subscale level or combine the two subscales to create a total hope score.

Screening, intervene and Train (SiT) intervention for Health Care Professionals

Version: 2.4

Date: 17/06/2020

